4 TRIAL DESIGN

This study will be a single centre, open labelled, randomised controlled trial comparing the effect of postoperative oral ferric maltol (intervention group) to standard care (control group), in patients with colorectal adenocarcinoma who have received pre-operative intravenous iron for anaemia. Each patient will be expected to participate for a period of 10 to 20 weeks, depending on the time between their diagnosis and the planned operation date. The participant will be recruited after the cancer MDT meeting confirming the diagnosis of colorectal adenocarcinoma and the ensuring that the patient is suitable for operative management. All study procedures will be undertaken at the time of existing hospital appointments where possible.

Recruitment will take place following the explanation of the cancer diagnosis by the clinical team. The patients will be asked by a member of the clinical or research team to state whether they consent to being approached by the research team for further information regarding the study. If they agree, a face-to-face conversation or a phone call to the patient will be arranged to discuss the research. A letter of invitation to participate in the trial (accompanied by a patient information leaflet) will then be given or posted to the patients. The patient will be given adequate time to consider participation in the study and they will be given the opportunity to ask any questions they may have. Patients who are eligible will then be invited to consent to the study.

After consenting to participate baseline data including demographics, past medical history and existing medications will be noted. Patients will be asked to complete the 3 quality of life questionnaires and they will have their blood taken including a full blood count, haematinics

(including iron, ferritin, transferrin and transferrin saturation) urea and electrolytes, liver function tests and erythropoietin. If the patients have consented to the optional sample sub-study, the patients may be asked to give other samples of faeces, urine, saliva or sweat. Following this visit the patient will receive their preoperative intravenous iron infusion as is standard care. If they are taking any existing oral iron supplementation they will be asked to stop this treatment prior to receiving their preoperative intravenous iron. Once the surgical procedure has been performed, tissue samples from the resected bowel may be obtained for analysis.

The participant is next reviewed when they are admitted on the morning of the operation.

Blood tests and the quality of life questionnaires will be repeated.

Preoperatively patients will undergo randomisation to one of the two study arms. After operation the participants haemoglobin will be checked on day 2 of their recovery. If, at this point, postoperative anaemia is confirmed they will enter into their study arm. The intervention group will commence a course of oral ferric maltol provided oral intake has recommenced and the control group will receive standard care. All patients will have blood tests checked again at day 3 and day 5 postoperatively if they remain as an inpatient. If they are found to be anaemic on either of these two blood tests they will, at this stage, enter their allocated treatment pathway. If a patient shows no evidence of anaemia on either day 2, 3 or 5 blood tests they will be withdrawn from the study. If the patients have consented to the optional sample sub-study, the patients may be asked to give other samples of faeces, urine, saliva or sweat at days 2, 3 or 5 along with the blood tests. Patients will continue treatment according to their randomisation allocation until 12 weeks after the operation, at which point the patient attends a routine surgical outpatient follow-up clinic. During the outpatient visit the participants will undergo their final blood and optional sample sub-study testing (if consented) as well as questionnaire completion.

The participants may only be required to attend the hospital for one extra visit to consent and where possible this will be arranged to coincide with existing appointments. The study is designed such that all other procedures are carried out when the participant attends for their routine visits as per the normal clinical pathway.

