7.7 Trial assessments

Following the consent process and baseline data collection the patient will attend for their preoperative iron infusion, as is routine care. They will then undergo the following trial assessments:

Day of Surgery (on the morning of their operation.):

- A brief interview will take place at the surgical pre-operative assessment ward to ascertain if the patient had any questions or if they experienced any side-effects in the intervening time. Any pre-operative blood transfusion will be noted. Information will be documented in the CRF.
- Blood will be drawn for the following tests: Full blood count, C reactive protein, iron, ferritin, transferrin, transferrin saturation, and erythropoietin.
- Optional sub-study urine, stool, saliva and sweat samples may be taken for analyses
- Grip strength may be recorded

- The participant will be requested to complete Quality of Life (QoL) questionnaires SF36, EQ-5D and FACT- An questionnaires.

Postoperatively they will be randomised to either the intervention group or the control group and the following assessments will be undertaken

Day 2 postoperatively.

- Information regarding the peri-operative period, intraoperative blood loss and any transfusion requirements will be documented in the CRF.
- Blood will be drawn for the following tests: Full blood count, erythropoietin, C-reactive protein, iron, ferritin, transferrin, transferrin saturation.
- Optional sub-study urine, stool, saliva and sweat samples may be taken for analyses
- Grip strength may be recorded
- At this point the Haemoglobin will be used to confirm postoperative anaemia (Hb <130g/L men, <120g/L women) allowing patients to commence their allocated treatment pathway according to randomisation.

Day 3 postoperatively.

- Blood will be drawn for the following tests: Full blood count, erythropoietin, C reactive protein, iron, ferritin, transferrin, transferrin saturation.
- Optional sub-study urine, stool, saliva and sweat samples may be taken for analyses
- Grip strength may be recorded

Day 5 postoperatively (if remains an inpatient).

- Blood will be drawn for the following tests: Full blood count.
- Optional sub-study urine, stool, saliva and sweat samples may be taken for analyses
- Grip strength may be recorded

Entry into postoperative treatment pathway

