If a patient is found to be not anaemic on day 2 postoperatively (Hb \geq 130g/L men, \geq 120g/L women) they will complete screening and remain in the study but will not enter their allocated treatment pathway (i.e ferric maltol or standard care). If they remain anaemic on day 3 or day 5 blood tests they will, at this stage, enter their allocated treatment pathway. If patients have a normal haemoglobin on days 2, 3 or 5 they will be withdrawn from the study.

Outpatient Follow Up

Finally, after discharge the patient will be seen in their first outpatient clinic at 8-12 weeks postoperatively. Where follow up occurs earlier, for example, due to the clinician's normal practice or due to a complication, then the usual 8-12 week outpatient visit will still be used.

At this visit the following assessments will be undertaken

- Information regarding postoperative complications, the length of hospital stay and readmissions to hospital will be documented in the CRF
- Any postoperative transfusion requirements will be documented in the CRF.
- Blood will be drawn for the following tests: Full blood count, erythropoietin, C-reactive protein, iron, ferritin, transferrin, transferrin saturation
- Optional sub-study urine, stool, saliva and sweat samples may be taken for analyses
- Grip strength may be recorded
- The participant will be requested to complete Quality of Life questionnaires: SF36, EQ-5D and FACT- An questionnaires.

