7.8 Withdrawal criteria

There will be intention-to-treat analyses carried out. Analysis of all participants who have been randomised will be undertaken regardless of withdrawal. The reason for withdrawal will

be recorded in the CRF. Each participant has the right to withdraw study at any time. A participant will be withdrawn from the study if any of the following occurs:

- Absence of anaemia on postoperative days 2, 3 and 5.
- Pregnancy
- Ineligibility (either arising during the study or retrospective having been inadvertently overlooked at screening)
- Significant protocol deviation as defined by the CI
- An adverse event which requires discontinuation of the study medication or results in inability to continue to comply with study procedures
- Disease progression which requires discontinuation of the study medication or results in inability to continue to comply with study procedures
- Patients who do not undergo an operation as a result of a change in fitness for surgery will be excluded.
- Consent withdrawn.
- Lost to follow up

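### The randomisation time is contradictory, and on either reading patients are randomised before the haemoglobin test that may then withdraw them by rule, with no clear place in the feasibility rates

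*Combined protocol and SAP*

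**What the plan says.** **Time of randomisation.** Section 4 (Trial Design): "Preoperatively patients will undergo randomisation to one of the two study arms". Section 7.7 (Trial assessments), after the morning-of-surgery items and before the day 2 items: "Postoperatively they will be randomised to either the intervention group or the control group". Section 7.3 gives no time; it says only that participants learn their arm after the operation. Appendix 1 has one mark for randomisation, at Visit 3, the day of surgery. The flow chart could not be seen in the copy reviewed.

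**Entry to the pathway.** Sections 4 and 7.7 use the postoperative Hb on day 2, or failing that day 3 or 5, to let a patient start the arm already allocated.

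**Patients who are not anaemic.** The rule appears three times:
- Section 4: "If a patient shows no evidence of anaemia on either day 2, 3 or 5 blood tests they will be withdrawn from the study".
- Section 7.7: "If patients have a normal haemoglobin on days 2, 3 or 5 they will be withdrawn from the study". Just before this, the same section says that a patient who is not anaemic on day 2 completes screening and stays in the study.
- Section 7.8: "Absence of anaemia on postoperative days 2, 3 and 5".

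The day 5 assessment in section 7.7 is headed "Day 5 postoperatively (if remains an inpatient)".

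**Analysis.** Section 7.8: "Analysis of all participants who have been randomised will be undertaken regardless of withdrawal". It adds that "The reason for withdrawal will" be recorded in the CRF. Section 10.3.2 lists screen failure, withdrawal (glossed as non-concordance) and retention as separate primary feasibility measures. Section 3.3.1 sets no feasibility criterion in advance and says that the data will inform the sample size of a definitive trial.

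**The concern.** Staff cannot follow both section 4 and section 7.7. The difference has a practical effect: a patient whose operation does not go ahead that morning is already randomised under section 4 but not under section 7.7.

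Whichever time applies, a condition for entering the treatment comparison is tested after allocation. Some randomised patients will therefore leave because the protocol removes them, although they declined nothing. The plan does not say under which feasibility measure they fall. Sections 4, 7.7 and 7.8 call them withdrawn, while section 7.7 also describes the day 2 result as part of screening. If they are counted as withdrawals, retention per randomised patient mixes a protocol-made exclusion with patient drop-out, and these rates are what the trial exists to estimate.

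Two gaps follow. The plan promises to analyse everyone randomised, but does not say which outcomes are collected on patients withdrawn by this rule. In addition, the three forms of the rule do not agree, so the status of some patients is undefined.

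**Working it through.** **Order of events.** Section 4 places randomisation before the operation and section 7.7 after it. Section 7.7 calls the surgery-day visit the morning of the operation, so the Appendix 1 mark leans towards preoperative. The tumour sample sits in the same column, however, so the mark is not decisive. Section 7.7 gives no hour for its postoperative randomisation, but lists it before day 2 and has the day 2 Hb release patients to their arm as randomised. Allocation therefore precedes the Hb check on both readings.

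**The withdrawal rule.** Sections 4 and 7.7 join the days with *or*; section 7.8 joins them with *and*. Read literally, the section 7.7 sentence withdraws the day-2 non-anaemic patient whom it has just kept in. Under section 7.8, a non-anaemic patient discharged before the inpatient-only day 5 test does not clearly meet the rule.

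**Size.** The plan has no figure to reproduce: section 10.1 makes no sample size calculation and sets 40 patients (20 per arm) from guidance that 30 or more suffice to estimate a parameter.

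Inputs:
- N = 40 (section 10.1).
- p = share without anaemia on days 2 to 5. The documents do not give it for patients treated with intravenous iron. Two assumed values come from section 1. The first is p = 10%, from the figure of up to 90% anaemic postoperatively, which was without intervention. The second is p = 25%, from the 75% still anaemic at operation after intravenous iron, a proxy measured before surgical blood loss.
- L = later loss among pathway entrants, assumed 10%.

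| Quantity | Formula | p = 10% | p = 25% |
|---|---|---|---|
| Withdrawn by rule | 40p | 4 | 10 |
| Pathway entrants expected | 40(1 − p) | 36 | 30 |
| Chance of fewer than 30 entrants | P(X ≤ 29), X ~ Bin(40, 1 − p) | 0.15% | 42% |
| Retention per randomised patient | (1 − p)(1 − L) | 0.90 × 0.90 = 81% | 0.75 × 0.90 = 67.5% |
| Retention per entrant | 1 − L | 90% | 90% |
| Share of attrition due to the rule | p / [p + (1 − p)L] | 0.10/0.19 = 53% | 0.25/0.325 = 77% |
| Consents for 40 randomised after the Hb check | 40/(1 − p), rounded up | 45 | 54 |

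The gap between the two retention rates is p(1 − L). For L from 5% to 20% it runs from 9.5 down to 8.0 points at p = 10%, and from 23.75 down to 20.0 points at p = 25%.

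**The case against.** **Classification.** A reader might infer that these patients will be reported as non-concordant. Section 10.3.2 does not say so. It lists screen failure separately, and the screening language in section 7.7 would allow them to be reported there. This objection stands: the defect is ambiguity, not a stated misclassification.

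**Planning.** A reader might infer that the definitive trial will be wrongly sized. If that trial keeps early randomisation, retention per randomised patient is the right planning figure. No document says that it will randomise later. This stands, and makes the harm conditional.

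**Analysis set and bias.** A reader might infer that these patients are dropped from the analysis, or that the exclusion biases the comparison. Section 7.8 keeps all randomised patients in the analysis. In patients who never enter a pathway, the deciding Hb is measured before any study drug, so exclusion does not depend on treatment received. Neither inference is supported. What remains is that analysing everyone randomised needs outcome data that the plan does not say it will collect.

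**Recoverability.** The reason for withdrawal is recorded and section 10.2 plans a descriptive analysis, so rates could be reported both ways without a redesign. This stands and limits the severity. It does not resolve the conflict over timing, which no later reporting can repair.

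**Conclusion.** The point holds in a limited form. Two parts are certain from the text: sections 4 and 7.7 contradict each other on when patients are randomised, and on either timing some patients are randomised and then withdrawn by rule. How those patients are counted is ambiguous.

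The size rests on assumptions. With 10% to 25% free of postoperative anaemia and 10% later loss, retention differs by 9 to 22.5 points according to the denominator. Neither value of p was measured on days 2 to 5 in patients like these, so the true share could lie outside the range. Numbers are a minor worry at 10% and a real one at 25%, where fewer than 30 entrants is close to an even chance.

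Because section 3.3.1 sets no criterion, no feasibility threshold is crossed. The harm is to the rates carried forward, and only if the definitive trial randomises at a different point. The plan should be changed, but the trial is not invalidated.

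**What to change.** State one randomisation time in sections 4, 7.3, 7.7 and Appendix 1.

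**Preferred.** Randomise after the first postoperative Hb that confirms anaemia as the protocol already defines it, and report patients without anaemia as pre-randomisation screen failures. The costs are:
- a protocol amendment (section 13.7 gives a response time of 35 days if it is substantial);
- about 5 to 14 extra consents for 40 randomised (45 − 40 and 54 − 40), plus any patients not operated on, at one centre within the 24-month trial period;
- shorter notice to pharmacy, which receives the randomisation alerts under section 7.3.

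Appendix 1 already places dispensing on days 2, 3 and 5.

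**If early randomisation is kept.** Say whether patients withdrawn by this rule are screen failures or withdrawals. Say which outcomes are collected on them, given the section 7.8 promise to analyse everyone randomised. Report withdrawal and retention with and without them. This costs wording and one extra line of reporting.

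**In either case.** Reconcile the *or* of sections 4 and 7.7 with the *and* of section 7.8, and state the status of a non-anaemic patient discharged before the day 5 test.

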10.5 Procedure to account for missing or spurious data

All attempts will be made to avoid and to recover any missing data. In the event of missing data being unrecoverable, a repeat sample may be taken in the case of a blood test. If this is

not possible (e.g. due to interventions being commenced), the participant will be excluded from the trial. Any unused or spurious data will be recorded in the CRF in the section for additional information.

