16. APPENDICES

16.1 Appendix 1 – Schedule of Procedures

Procedures	Screening	Baseline	Treatment Phase				Follow Up
	Visit 1	Visit 2	Visit 3 Day of surgery	Visit 4 Day2	Visit 5 Day 3	Visit 6 Day 5	Vist 7 8-12 weeks
Screening	X						
Informed consent		X					
Demographics		X					
Medical history		X					
Concomitant medications		X					
Eligibility assessment	X						
Randomisation			X				
Dispensing of trial drugs				(X)	(X)	(X)	
Blood Sample		X	X	X	X	X	X
Urine Sample*		X	X	X	X	X	X
Tumour Sample			X				
Paraffin embedded sections							X at a later date
Faeces/stool sample*		X	X	X	X	X	X
Saliva sample*		X	X	X	X	X	X
Sweat sample*		X	X	X	X	X	X
QoL questionnaire completion		X	X				X
Grip Strength			X	X	X	X	X
Adverse event assessments		X	X	X	X	X	X
CRF Data collection		X	X	X	X	X	X
Physician's Withdrawal Checklist		X	X	X	X	X	X

*If consented for sample sub-study.

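### Section 4 limits the day-3 blood test to inpatients and section 7.7 does not, so a patient home before day 3 is complete under one section and has a missed sample under the other

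*Combined protocol and SAP*

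**What the plan says.** Four parts of the combined protocol and SAP bear on the day-3 test, and a fifth on who is analysed.

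- **Section 4 (Trial design):** "All patients will have blood tests checked again at day 3 and day 5 postoperatively if they remain as an inpatient". One condition follows both days.
- **Section 7.7 (Trial assessments):** one block is headed "Day 3 postoperatively", with no condition. The next is headed "Day 5 postoperatively (if remains an inpatient". The day-3 block lists full blood count, erythropoietin, C-reactive protein and the iron markers; the day-5 block lists full blood count only.
- **Appendix 1 (Schedule of procedures):** the blood sample row is marked at both day 3 and day 5. The only footnote, "If consented for sample sub-study", concerns the optional samples and not inpatient status.
- **Section 10.5 (missing or spurious data):** "In the event of missing data being unrecoverable, a repeat sample may be taken in the case of a blood test". If a repeat is "not possible (e.g. due to interventions being commenced), the participant will be excluded from the trial".
- **Section 7.8 (Withdrawal criteria):** "Analysis of all participants who have been randomised will be undertaken regardless of withdrawal".

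**The concern.** Whether a day-3 sample was due decides whether its absence counts as missing data. For a patient who goes home before day 3, sections 4 and 7.7 answer differently, and three things depend on the answer.

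1. **Feasibility reporting.** Section 10.3.2 counts completeness of the outcome measures among the primary feasibility outcomes. If day-3 bloods enter that count, the denominator depends on which section is followed. Day 3 is also the last planned measurement of the iron markers before the 8–12 week visit, and these markers are a secondary endpoint in section 3.3.2.
2. **Who stays in the trial.** A sample that counts as missing falls under section 10.5, which ends in exclusion when no repeat can be taken. Section 7.8 keeps every randomised participant in the analysis.
3. **Balance between arms.** The example in section 10.5 of a repeat that cannot be taken is that an intervention has begun. A ferric maltol patient found anaemic on day 2 may have started capsules by day 3, while a control patient has no study drug to start. Applied literally, the rule could fall more heavily on the ferric maltol arm. This is an inference from the wording; the plan does not state it.

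**Working it through.** The plan gives no figure to reproduce: section 10.1 makes no sample size calculation, and no discharge times appear anywhere. The check is a comparison of the texts, followed by an illustration.

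**Step 1: a patient discharged before day 3**

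| Source | Inpatient condition on day 3 | Inpatient condition on day 5 | Status of the absent day-3 sample |
|---|---|---|---|
| Section 4 | Yes | Yes | Not called for |
| Section 7.7 | None stated | Yes | Missed |
| Appendix 1 | None stated | None stated | Missed if taken at face value |

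The firm conflict is between the first two rows. Appendix 1 is weak evidence for either side. It also leaves day 5 unconditional, although sections 4 and 7.7 both restrict day 5, so it may simply omit inpatient conditions.

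**Step 2: what follows if the sample is missed**

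Section 10.5 first allows a repeat blood test. Only if that cannot be done does it exclude the participant. Section 4 plans for procedures after the consent visit to coincide with routine attendances, so no special day-3 return after discharge is foreseen. Exclusion is therefore a possible result of a literal reading, but not an automatic one, and it contradicts section 7.8.

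**Step 3: illustration of size**

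Inputs: N = 40 (section 10.1). The share discharged before day 3 is an assumption of 5%, 10% or 20%, and everyone else is taken to be sampled. With x patients discharged before day 3:

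- completion under section 4 = (40 − x)/(40 − x) = 100%
- completion under section 7.7 = (40 − x)/40

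| Assumed share | x | Section 4 | Section 7.7 | Left in trial if all x were excluded |
|---|---|---|---|---|
| 5% | 0.05 × 40 = 2 | 100% | 38/40 = 95% | 38 |
| 10% | 0.10 × 40 = 4 | 100% | 36/40 = 90% | 36 |
| 20% | 0.20 × 40 = 8 | 100% | 32/40 = 80% | 32 |

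Each such patient moves day-3 completion by 1/40 = 2.5 percentage points. The last column is a worst case, with no repeat possible for anyone. The total would fall below the 30 that section 10.1 cites as sufficient only with 11 or more exclusions (40 − 11 = 29; 11/40 = 27.5%), which is outside the illustrated range.

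**The case against.** The best reply is that the documents, read as a whole, already point to one meaning. Because no extra attendance is planned after discharge, the day-3 block in section 7.7 may only list what is drawn on the ward. Alternatively, the condition in section 4 might be read as governing day 5 alone, which would agree with section 7.7. Both readings are possible. But section 7.7 states the condition for day 5 and leaves it off day 3, and the natural reading of section 4 covers both days. Site staff should not have to choose between them.

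The reply is stronger on consequences, and several inferences that a reader might draw are not supported:

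- **That early leavers will be excluded.** Section 10.5 mentions neither discharge nor day 3, offers a repeat first, and is opposed by section 7.8. For the same reason, the plan cannot be said to remove the shortest stays and so distort length of stay.
- **That the conflict creates withdrawal on a single test.** Uncertainty over a patient who is not anaemic on day 2 and then goes home comes from the withdrawal wording in sections 4, 7.7 and 7.8. It would remain if the day-3 rule were settled: a non-anaemic patient discharged on day 4 has no day-5 result under either section.
- **That the background anaemia figure gives the number of changed entry decisions.** Section 1 gives up to 90% without intervention. That is an upper bound in untreated patients, and these participants receive preoperative intravenous iron, so it does not imply that 10% are non-anaemic here.

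It is also fair to say that the analysis is descriptive, that section 10.3.3 names no day-3 comparison, and that section 10.3.2 does not say day-3 bloods count towards completion.

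**Conclusion.** The inconsistency between sections 4 and 7.7 is real, and it leaves the status of a day-3 sample undefined for any patient discharged before that day. Section 10.5 attaches a possible exclusion to that status, contrary to section 7.8. The point is minor.

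Its size cannot be established from the documents. The range of 2 to 8 patients, with day-3 completion of 95% to 80% against 100%, rests entirely on an assumed 5% to 20% discharged before day 3, and the true number could be lower. The possible imbalance between arms is likewise an inference from one example in section 10.5.

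A reader might conclude that section 4 has the right schedule, because section 7.7 cannot be met without a return visit. The documents do not settle that, and the choice is for the sponsor.

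**What to change.** 1. Reconcile section 4, section 7.7 and Appendix 1 on who is due the day-3 blood test, and state the same condition in all three. In Appendix 1, also show the inpatient condition that sections 4 and 7.7 already place on day 5. Which day-3 rule to adopt is for the sponsor.
2. Align section 10.5 with section 7.8: a day-3 or day-5 blood sample not taken because of discharge does not remove a randomised participant from the analysis.
3. For each of days 2, 3 and 5, report by arm the number of participants due a sample and the number sampled, so that completion can be read whichever rule is chosen.

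The cost is wording in three places, one sentence in section 10.5 and one descriptive table. The sample size is unchanged. No extra visit arises unless the sponsor decides that a day-3 sample is required after discharge.
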